One theory-driven approach that has shown promise as a basis for intervention development is cognitive dissonance induction. Cognitive dissonance theory is based on the premise that individuals strive toward consistency between their beliefs and behaviors.⁷ When *inconsistencies* between attitudes, beliefs or behaviors occur, individuals tend to adjust their beliefs or behaviors in order to reduce the discomfort of the dissonance that is elicited by the inconsistency. Reducing cognitive dissonance can be achieved in one of three ways: 1) adjusting one or more attitudes or behaviors to make the relationship between the two consistent, 2) acquiring new information that offsets the dissonant belief, or 3) reducing the importance of the attitudes or beliefs so that the inconsistent behavior can continue.

Interventions that use cognitive dissonance to elicit behavior change do so through situations that create high levels of cognitive dissonance. Regardless of the behavior being targeted, there are several common concepts that are central to effective cognitive dissonance induction. First, participation in the induction activity must be voluntary. Voluntary participation requires the individual to attribute the inconsistency between beliefs and behaviors as existing within themselves, rather than being due to demands of a given situation.⁷ Effortful involvement (i.e., actively engaging in treatment exercises) is also required, and is believed to result in greater dissonance and greater motivation for change.³⁰ And finally, public statements of beliefs (i.e., counter-attitudinal advocacy) are thought to elicit heightened dissonance responses.³¹ In fact, Roehrig et al³² have shown counter-attitudinal advocacy to be successful in isolation of the other dissonance-inducing components (voluntariness, effortful involvement). Counter-attitudinal advocacy activities that are often used to induce dissonance include preparing and delivering speeches or statements about personal beliefs, role-plays where individuals act out a particular behavior, or making public commitments. Given the central role that counter-attitudinal activities appear to play in eliciting cognitive dissonance, these activities are a core component of the proposed cognitive dissonance mobile app intervention (CDI).

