D.4.2.a. Participants. Details regarding sample characteristics, eligibility criteria, recruitment and retention are described in the Human Subjects. Briefly, participants will include both male and female adult smokers recruited from the United States. We have a long history of successful recruitment of smokers, and have

extensive experience utilizing recruitment efforts to enroll smokers and tobacco users in mobile app-based intervention programs. Inclusion criteria will be as follows: 1) age 18 or older, 2) self-reported daily smoking, 3) having a valid home mailing address, 4) English-speaking, 5) access to a smartphone with video capability for the duration of the project, 6) not currently enrolled in or participating in any tobacco cessation programs, and 7) expressed desire to quit smoking.

D.5. Data Collection Procedures

D.5.1. Overview and timeline for the pilot study. In the proposed evaluation study, a total of 60 participants will be recruited and baseline assessed during Year 1. We anticipate that approximately 10-25% of these will fail to complete the study; however, we will employ an intent-to-treat analysis strategy, which will include all participants. We will conduct baseline assessments immediately after enrollment and consent; all measures completed at 1-, and 3-month follow-up assessments will be provided online.

The baseline assessment will primarily measure participant risk factors, as well as past and current cigarette and other tobacco use, readiness to quit, quit attempts and cessation in the past year, and will consist of questionnaires administered using Qualtrics; none of the assessments will be done via the mobile app.

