The 1-month assessment will focus on usability, cognitive dissonance, motivation to quit, and short term outcomes such as making a quit attempt, use of the app (dosage), number of cigarettes smoked, and days abstinent from smoking. For the 3-month assessment, the focus will be on cessation outcomes, including both point prevalence (i.e., no smoking in the past 7 days; no smoking in the past 30 days) and sustained abstinence, which is defined as sustained abstinence between the 1- month and 3- month assessment. We will also assess quit attempts at each assessment. Non-responders to the request to complete a follow up assessment will be sent email and text messages to encourage completion of the assessment. We will continue to prompt completion for 14 days following the initial request for the one month assessment and there will be a 30 day window for completion of the 3-month assessment.

D.5.2. Pilot Study Measures. Program navigation and usability will be assessed during usability testing and for the evaluation participants over the one month of use, and will include reports of: 1) ease of use, 2) perceived benefits of using the app, and 3) suggestions for product development modifications. Participants will also provide ratings on product satisfaction and usability on a 7-point Likert Scale. Qualitative data gathered from the focus groups will be recorded and evaluated with the goal of identifying challenges to using the app, product satisfaction, and suggested modifications. This information will then be used to guide adaptations in a Phase II SBIR application. In addition to qualitative data, login tracking information from the app will be used to assess each participant's: 1) frequency and duration of app use, 2) number of modules completed, and 3) type and frequency of substance use. These data will be used to evaluate treatment engagement and adherence, as well as pre- and post- changes in tobacco use.

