A full description of measures is included in the Human Subjects. Briefly, the following will be used to examine pre- and post- changes in smoking behavior, cognitive dissonance, and motivation to quit: 1) Nicotine Dependence, 2) Past and Current Tobacco Use, 3) Motivation to Quit, 4) Quit Attempts, and 5) Cognitive Dissonance. Nicotine dependence will be measured at baseline and at each follow-up assessment using the Fagerström Test for Nicotine Dependence⁵⁸ and items that assess withdrawal experiences. Past and current tobacco use will be assessed at each time point, including type, frequency, and duration of use. Motivation to quit will be assessed at baseline by asking participants if they want to quit within the next 30 days and at follow-up assessments in terms of stages of change.⁵⁹ We will also use an adaptation of the Contemplation Ladder⁶⁰ that we have used extensively in our prior research^{40,61} and have found in predicting tobacco cessation.^{61,62} Quit attempts will be measured by the number of intentional quit attempts that last at least 24 hours, duration of quitting, and use of pharmacological adjuncts at each time point. Cognitive dissonance will be measured using the Dissonance Thermometer.^{63,64} Prior research⁶³ has shown that the 3- item discomfort factor of the Dissonance Thermometer represents the affective expression of cognitive dissonance.

D.5.3. Statistical Design and Power Overview.

This project will test the *promise* of efficacy of the CDI mobile app with a pre-training, post-training, and 3- month follow-up non-experimental design with 60 adult daily smokers. We hypothesize that after use of the CDI mobile app participants will show increases in quit attempts and number of non-smoking days, and improvement in smoking attitudes and behaviors. We will use random effects growth models to test change in normally distributed outcomes and the Wilcoxon signed-rank test for non-normally distributed outcomes. We also propose ancillary analysis (e.g., dose-response) to bolster our confidence in the non-experimental design. Details of our analytic approach, approach to missing data, power analysis (power >.80 to detect medium effects ($d=.39$) for pre-post change), and feasibility benchmarks are provided in Statistical Design and Power in the Human Subjects.

Reference List

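### Dose-response on self-chosen app use cannot add causal confidence to a single-arm pilot: it could show a gradient in either direction even if the app does nothing

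*Combined protocol and SAP*

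**What the plan says.** D.5.3 describes a "follow-up non-experimental design with 60 adult daily smokers", with no comparator. Dose-response is given as an example of ancillary work, and its purpose is stated: "ancillary analysis (e.g., dose-response) to bolster our confidence in the non-experimental design".

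Dose is observed, not assigned. D.5.2 takes from the app log "1) frequency and duration of app use, 2) number of modules completed". In D.5.1 the 1-month assessment covers "use of the app (dosage), number of cigarettes smoked, and days abstinent from smoking", so use and smoking are collected together. B.2 makes choice part of the theory: "First, participation in the induction activity must be voluntary".

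The supplied text does not say which dose variable, outcome, model, lag or covariates the dose-response analysis will use. It refers the reader to the Human Subjects section for analytic detail, and that section is not in the supplied text.

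**The concern.** The analysis is asked to make up partly for a missing control group. A gradient across assigned dose levels could do that; a gradient across self-chosen use cannot, for three reasons.

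- **Motivation.** A more motivated smoker may both use the app more and smoke less. D.5.2 accepts half of this path, since it says the adapted Contemplation Ladder predicts cessation.
- **Relapse.** Someone who relapses may stop opening the app, so smoking drives use.
- **Success.** Someone who has quit may also stop opening it, which pushes the gradient the other way.

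At stake is how the pilot is read. Aim 3 uses changes in smoking outcomes to judge efficacy and the case for Phase II, and B.2 already suggests that more exposure might improve abstinence. A positive gradient would fit that expectation and could be taken as confirmation. A negative one could be taken, just as wrongly, as evidence against the app.

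**Working it through.** **1. The plan's own figure.** D.5.3 gives "power >.80 to detect medium effects ($d=.39$) for pre-post change". Alpha is not stated; I assume 0.05 two-sided. Normal approximation at N = 60: 0.39 × √60 − 1.96 = 3.021 − 1.96 = 1.061, so power is Φ(1.061) = 0.856. The paired t-test gives 0.844, so the figure reproduces. D.5.1 says "We anticipate that approximately 10-25% of these will fail to complete the study", which leaves 54 to 45 completers, with power 0.803 and 0.725. This figure concerns pre-post change; no figure is given for the dose-response analysis. I use n = 54 below.

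**2. Model with no app effect.** All variables are standardised, M is motivation, and e and u are independent noise.

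- Outcome (higher is better): Y = bM + √(1 − b²)·e
- App use: U = aM + f·e + √(1 − a² − f²)·u

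Here a and b are the motivation paths to use and to outcome. Feedback f is positive if relapse reduces use and negative if success reduces use. The app has no path to Y. The implied correlation is ρ = ab + f√(1 − b²). The chance of a significant positive gradient is about Φ(atanh(ρ)·√(n − 3) − 1.96), with √51 = 7.141. The nominal value in one direction is 2.5%.

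The documents give none of a, b or f. Every value is an assumption, shown as a range.

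**3. Unadjusted results, n = 54.**

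| a, b, f | ρ | Formula | Simulated (20,000 trials) |
|---|---|---|---|
| .2, .2, 0 | .040 | Φ(0.286 − 1.96) = .047 | 4.6% |
| .3, .3, 0 | .090 | Φ(0.644 − 1.96) = .094 | 9.4% |
| .4, .4, 0 | .160 | Φ(1.152 − 1.96) = .210 | 21.0% |
| 0, .3, .2 | .191 | Φ(1.380 − 1.96) = .281 | 28.1% |
| 0, .3, .3 | .286 | Φ(2.103 − 1.96) = .557 | 56.3% |
| .3, .3, .3 | .376 | Φ(2.826 − 1.96) = .807 | 81.2% |
| .3, .3, −.3 | −.196 | negative direction: Φ(1.420 − 1.96) = .294 | 29.3% negative, 0.1% positive |

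In the first row the two-sided rate is 5.8%, close to the nominal 5%. In a milder version, relapse feedback of .3 acts only on later use. The two-sided rates are then 45% (motivation paths of .3) and 62% (paths of .4). With 45 completers the pattern is the same and a little weaker: 8.5% for motivation .3, 49% for relapse .3, and 73.5% for both.

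**4. Adjusting for baseline motivation** (score reliability 0.64, n = 54). The motivation-only rates at .3 and .4 fall from 9.4% and 21.0% to 4.4% and 6.6%. The relapse-only rate at .3 does not fall: 56.3% unadjusted, 58.3% adjusted. With both mechanisms at .3 it goes from 81.2% to 70.6%. A baseline covariate cannot remove feedback that arises after baseline.

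**5. Early-window dose, later outcome, adjusted** (score reliability 0.8, n = 54). If relapse does not act inside the window, the two-sided rate is 5-6%. If early smoking affects early dose at .3, the rate depends on the residual correlation between early and later smoking:

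| Residual correlation | Motivation paths .3 | Motivation paths .4 |
|---|---|---|
| .3 | 12% | 16% |
| .5 | 22% | 26% |
| .7 | 36% | 41% |

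These values move by a few points with the way the feedback path is scaled.

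**The case against.** The strongest reply has five parts.

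- **Not inevitable.** A reader might infer that the analysis would show a dose effect whatever the app does. The documents do not support that. With weak motivation paths and no feedback, error is near nominal. Eligibility requires a wish to quit (D.4.2.a), which may narrow the spread of motivation. The large figures rest on a feedback path that no document states. This part stands: the right word is could.
- **Sign unknown.** If quitters stop using the app, a positive result almost never appears. This also stands, but it does not rescue the analysis: with no app effect the test can go either way, so neither sign informs efficacy.
- **A lagged analysis is not excluded.** A reader might infer that 1-month use will be tested against 1-month smoking. No outcome is named. The 3-month outcomes, including abstinence between the 1- and 3-month assessments, follow the month of use. This stands, and the fix builds on it.
- **Detail is elsewhere.** The section is an overview, and the missing Human Subjects text may contain a lag and covariates. That is possible. However, adjustment leaves the relapse path intact, and a lag leaves relapse within the dose window.
- **Modest role.** The analysis is ancillary, the pilot claims only promise of efficacy, and aim 3 ties Phase II to changes in smoking outcomes. A reader might infer that dose-response decides the move to Phase II; the documents do not say so. The point is therefore about interpretation, not a flaw in the main analysis.

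**Conclusion.** The point holds as stated in the heading. The stated purpose of the analysis, added confidence in an uncontrolled design, is not one that self-selected use can serve. With no app effect and 54 completers, the chance of a significant gradient runs from 5.8% two-sided (motivation paths of .2, no feedback) to well over 40% with relapse feedback of .3: 45-62% if feedback acts on later use only, and 56-81% in the positive direction if it acts on all use. A success path of −.3 gives a significant negative gradient in 29%. These figures show what could happen. They are not forecasts, because every path strength is assumed.

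A reader might also infer that an early window plus adjustment restores the nominal error rate. It does so only if relapse does not act inside the window; otherwise about 12-41% remains under the values tried. The better method reduces the bias but does not make the result evidence of efficacy. Whether the Human Subjects section already specifies part of this cannot be judged from the supplied text.

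**What to change.** 1. Pre-specify one dose measure from the app log in a fixed early window, for example modules completed in the first 14 days.
2. Relate it only to smoking after that window, for example abstinence between 1 and 3 months or the 3-month outcomes.
3. Adjust for baseline nicotine dependence, cigarettes per day and motivation. D.5.2 gives the Contemplation Ladder no time point, so confirm that it is collected at baseline, or use the baseline question on quitting within 30 days.
4. Replace the stated purpose in D.5.3 with a statement that the result is a descriptive association and not evidence of efficacy, and say why: self-selection, and relapse or quitting that may change use, including inside the early window.
5. If the Human Subjects section already covers any of these, bring D.5.3 into line with it.

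The cost is analysis wording and one check on the timing of the Ladder; the log and smoking data are already planned. The downside is that later app use is left out of the dose. Causal support would need a randomised comparator or randomised dose, which could be a matter for Phase II.

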3. Evaluate the prototype app by having 60 daily adult smokers recruited through social media to complete the first 3 modules. Usability data, system log data on program use, and participant satisfaction data will also be analyzed. Input from participants will be gathered to incorporate additional features to be developed during Phase II. Significant changes in quit attempts, number of days without smoking (smokefree days) and changes in smoking attitudes and behavior will be used to determine the efficacy of the Phase I program and evidence for proceeding to Phase II development and evaluation.

B. SIGNIFICANCE

B.1. Importance of smoking cessation

Smoking is the leading cause of preventable death in the U.S.,^{1,2} accounting for approximately 443,000 deaths, which is 20% of all deaths annually.^{1,23} Despite overall declines in the rate of tobacco use in the United States over the past 30 years, improving quit rates among current smokers continues to be a significant public health focus given the high risk for long-term negative health outcomes.² There has been extensive research evaluating a wide range of smoking cessation approaches over the past 40 years, and the 2008 Clinical Practice Guideline for treatment of tobacco use and dependence summarized the efficacy of smoking cessation approaches based on more than 8700 research articles. Although there has been significant progress in the application of both clinical and public health interventions aimed at smoking cessation, researchers have concluded that the overall success rate of these interventions has not shown significant improvement.³ New, innovative, theory-driven approaches are needed to both improve the overall abstinence and long-term quit rates, as well as to increase the reach of effective interventions.

B.2. Cognitive Dissonance-based intervention approaches

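### Does the stated power of more than .80 for d=.39 fail once the plan's own 10-25% loss is allowed for?

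*Combined protocol and SAP*

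**What the plan says.** Section D.5.3 (Statistical Design and Power Overview) describes an uncontrolled design with a baseline, a post-training assessment and a 3-month follow-up in 60 adult daily smokers. It states "power >.80 to detect medium effects ($d=.39$) for pre-post change". The sentence is a summary that points elsewhere: the analytic approach, the handling of missing data, the power analysis and the feasibility benchmarks "are provided in Statistical Design and Power in the Human Subjects". That section is not part of the text available here.

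The same section assigns random effects growth models to normally distributed outcomes and the "Wilcoxon signed-rank test for non-normally distributed outcomes".

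Section D.5.1 says "a total of 60 participants will be recruited and baseline assessed during Year 1", then: "We anticipate that approximately 10-25% of these will fail to complete the study". It adds that "we will employ an intent-to-treat analysis strategy, which will include all participants". Follow-up is at 1 and 3 months, and section D.5.2 speaks of usability being assessed "for the evaluation participants over the one month of use", which suggests that month 1 is the post-training visit.

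Aim 3 in section A says that significant changes in quit attempts, smokefree days and smoking attitudes and behaviour "will be used to determine the efficacy of the Phase I program and evidence for proceeding to Phase II development and evaluation".

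**The concern.** A single power figure stands beside a wide range of expected loss, and nothing in the overview links the two. Losing 10-25% of 60 leaves 54 to 45 participants with complete data. Under the usual conventions, 54 is the smallest number of pairs that gives power above .80 for d=.39, so the claim would hold only at the favourable end of the plan's own range. The intent-to-treat statement does not repair this: keeping a participant in the analysis set supplies no observed change for someone who never answers a follow-up.

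Aim 3 counts significant change towards the case for Phase II. Under the same conventions the chance of missing a true d=.39 on one outcome is 0.20 at 10% loss and 0.27 at 25%. A useful product could look unpromising because of poor retention, and a reader of the overview would not have been warned.

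**Working it through.** **Inputs from the documents.** Enrolment is 60 and loss is 10-25% (D.5.1). The effect is d=.39 for pre-post change and the claimed power is above .80 (D.5.3).

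**Inputs assumed, because the available text does not give them.** Two-sided alpha 0.05, d standardised by the SD of the change score, and analysis of complete pairs by a paired t-test.

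**Formula.** Power = P(|T| > t(0.975, n−1)), where T is noncentral t with n−1 degrees of freedom and noncentrality d√n.

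**Step 1: the plan's figure.**

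| Pairs n | Origin | d√n | Critical t | Power at d=.39 | d detectable at 80% power |
|---|---|---|---|---|---|
| 60 | no loss | 3.021 | 2.001 | 0.844 | .368 |
| 54 | 60 × 0.90 | 2.866 | 2.006 | 0.803 | .388 |
| 53 | – | 2.839 | 2.007 | 0.796 | .392 |
| 45 | 60 × 0.75 | 2.616 | 2.015 | 0.725 | .427 |

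The claim reproduces at 60 and at 54, and 54 is the smallest n that meets it. The last column is also informative: a calculation that ignored loss would have given .37, whereas .39 is the rounded value at 54 pairs. This is only inference, but it fits a calculation that already allowed for 10% loss.

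**Step 2: does the shortfall at 45 survive a change of assumption?** Each line changes one assumption.

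- *One-sided 0.05.* The hypotheses in D.5.3 are directional. Critical t at 45 pairs falls to 1.680 and power is 0.824.
- *d on the raw SD.* The effect on the change scale is then .39/√(2(1−r)), where r is the pre-post correlation. At r = 0.3, 0.5, 0.6 and 0.7 this is .330, .390, .436 and .503. Power at 45 pairs is 0.58, 0.73, 0.82 and 0.91, and it reaches .80 at r of about 0.58. This assumption can cut either way: on this metric even 60 pairs need r of about 0.44.
- *Timing of loss.* The 10-25% is failure to finish the study, which runs to month 3. If the powered contrast is baseline to month 1, a participant lost after month 1 still gives a pair. With 15 non-completers (60 × 0.25), 9 answering at month 1 give 45 + 9 = 54 pairs and power 0.803.
- *Use of both follow-ups.* Suppose the three visits have equal variance and equal correlation, and the effect is sustained. The variance of (mean of two follow-ups − baseline) is 1.5σ²(1−r), against 2σ²(1−r) for a single change. The standardised effect becomes .39 × √(2/1.5) = .450, and power at 45 is 0.84. This is a different contrast from a single pre-post change, but it shows what a three-wave model can recover.

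**Step 3: what stays open.** At 45 pairs the readings above run from 0.58 to 0.91. The documents available here do not say which applies.

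**The case for a change.** The strongest case for a change is that the figure cannot be interpreted as printed. Without alpha, sidedness, standardiser and analysed number, a reader cannot tell whether power at 25% loss is 0.58 or 0.91. The value .39 itself hints that only the 10% end was used. Quit attempts and smokefree days are counts, so they may go to the signed-rank test, which works on pairs and gains nothing from a growth model's use of partial data. Stating the inputs would take one sentence and no extra participants.

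Part of this stands. The overview would be more useful with its inputs beside the figure and with the post visit and its expected loss named. But D.5.3 sends the reader to another section for exactly this material, and its absence from a one-sentence summary is not evidence that it is absent from the plan. The signed-rank point shows where complete pairs would matter, but not by how much: the plan keeps that test for non-normal outcomes, and the available text gives no distribution from which to compute its power.

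One might also ask for time to be fitted as a category, since a straight line over 0, 1 and 3 months can lose power when an effect arrives early and then levels off. D.5.3 does not say that time is linear or how it is coded, so that is a modelling preference, not a correction.

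**Conclusion.** The concern does not call for a change. The claimed power is reproduced at 60 pairs (0.844) and at 54 pairs (0.803), assuming two-sided 0.05 and d on the SD of change. The documents do not show it to be wrong. It drops to 0.725 only if loss reaches 25%, all of that loss falls before the post visit, only complete pairs inform the test, and those two assumptions hold. A one-sided test, a raw-SD d with a correlation of about 0.58 or more, at least 9 of 15 non-completers answering at month 1, or a sustained effect estimated from both follow-ups would each bring power to .80 or above. A raw-SD d with a low correlation would push it the other way.

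Even on the least favourable retention, under the conventional inputs, the detectable effect moves only from .39 to .43. The trial is a pilot of the promise of efficacy. Aim 3 looks at several outcomes alongside usability, log and satisfaction data, so the 0.20 or 0.27 chance of a miss describes one test and not the Phase II decision. What remains is missing detail in an overview that refers to a fuller section. Supplying it would alter no sample size, analysis or result.
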